2 BACKGROUND INFORMATION AND SCIENTIFIC RATIONALE

2.1 Background Information

The natural history of congenitally acquired CMV infection is well described.¹⁻⁷ In contrast, outcomes of perinatally and postnatally acquired CMV infections are less well characterized. It is generally agreed that postnatal acquisition of CMV in term infants does not lead to symptomatology or disease.⁸ In preterm infants, initial case reports suggested that peri- and postnatally acquired CMV infections could produce severe disease.⁹⁻¹⁴ Larger series and case-controlled trials more recently suggest that symptomatic disease in preterm babies is less common than asymptomatic infection, and long-term sequelae are rare.¹⁵⁻¹⁹ Nevertheless, severe disseminated CMV disease can occur in premature infants, including life-threatening pneumonitis, hepatitis, and thrombocytopenia.²⁰ Antiviral therapy in such patients is frequently used, albeit without either controlled data to demonstrate benefit or knowledge of proper dosing regimens.¹² In patients with symptomatic congenital CMV disease, six weeks of intravenous ganciclovir improves hearing outcomes in early childhood,²¹ and may benefit neurodevelopmental outcomes as well.²² In premature babies with visceral disease from postnatally acquired CMV, the goal of antiviral therapy is different; namely, it is to treat the end-organ disease, which is occurring at that time, rather than to prevent or improve long-term sequelae. Without efficacy data, the duration of treatment is variable, but anecdotal experience suggests that it generally is in the range of two to four weeks of total antiviral therapy. Approximately two-thirds of treated neonates receiving six weeks of intravenous ganciclovir develop Grade 3 or 4 neutropenia (utilizing the DAIDS Toxicity Tables) during therapy.²¹

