With the receipt of one of the Study Assessment Doses (dose 3, 4, 5, 6, 7, or 8) of intravenous ganciclovir, pharmacokinetic specimens will be obtained at 0h (immediately prior to IV ganciclovir dose; window: -15 min), 1h (immediately after the end of the IV ganciclovir dose; window: +15 min), 2-3h, 5-7h, and 10-12h. This complete set of pharmacokinetic time points will allow for the AUC and clearance (CL) to be calculated in each subject. Specimens will be shipped to the UAB Antiviral Pharmacology Laboratory for processing at that time. The pharmacokinetic data will then be provided to the study site, including the AUC and CL values,

for information purposes. The decision of whether or not to adjust the dose will be a clinical one to be decided by the treating physician, and will not be dictated by the research protocol. The parameters for AUC and CL from prior CASG ganciclovir^{27,30} and valganciclovir^{25,29} studies demonstrate that these PK parameters may be useful in guiding dose adjustments. Duration and dose of intravenous ganciclovir therapy is made at the discretion of the treating physician and will not be dictated by the research protocol.

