Both whole blood for CMV PCR and urine for CMV assessment will be obtained serially through Study Assessment Period 7 as long as the subject is receiving intravenous ganciclovir therapy (that is, until the ganciclovir is permanently discontinued). These specimens will be used to determine viral load and, as indicated, ganciclovir resistance. At each sample collection time, urine will be split into two aliquots. These aliquots will be available for CMV detection as appropriate, based upon whole blood viral loads. Specimens will then be available for subsequent testing for ganciclovir resistance in the UAB Virology Resistance Laboratory. Since ganciclovir is a renally excreted drug, serum creatinine will be drawn for the research protocol on the day that the ganciclovir pharmacokinetic specimens are obtained in order to calculate creatinine clearance using a method such as the modified Schwartz formula, and thus correlate ganciclovir clearance with renal function. Otherwise, data from hematology assessments (WBC count and differential, hemoglobin, platelet count) and from chemistry labs (serum creatinine, ALT, and AST) will be recorded on the study case report forms each study assessment period if they are being obtained for clinical reasons, but will not be drawn only for the purposes of the study. Ganciclovir dosing information (mg/dose, dosing interval, and subject weight) will be recorded on the day of the pharmacokinetic blood draws. Once a subject is successfully enrolled into the study the ganciclovir dosing information (mg/dose and dosing interval) will be recorded from the start of clinical treatment of ganciclovir until date of enrollment. After enrollment ganciclovir dosing information (mg/dose and dosing interval) will be captured from Study Assessment Period 1 through the Study Assessment Period 7; as long as the subject is receiving intravenous ganciclovir therapy.

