7.4 Final Study Visit

7.4.1. Period 7 (Study Assessment Day 39 through Study Assessment Day 42)

Documentation of receipt of PRBC transfusion(s) will be provided on an eCRF. If the study subject has NOT received ≥ 10 PRBC transfusions (see Section 9.3.1), proceed with required assessments.

Required assessments [following confirmation that subject is still receiving ganciclovir (e.g., that the ganciclovir has not been permanently discontinued)]: 1) virology blood specimens for CMV viral load (required amount of whole blood for CMV PCR is 0.5 mL); 2) CMV detection from noninvasive urine specimen (if obtainable); 3) ganciclovir dosing information (mg/dose, dosing interval, subject weight).

Optional assessments (if being drawn for clinical reasons; any laboratory value obtained during the window will suffice, with an effort being made to capture the most abnormal value): 1) hematology labs (WBC with differential, hemoglobin, platelet count); 2) chemistry labs (AST, ALT); 3) Serum creatinine.

Study Assessments (as described)	Optional Assessments*
Virology blood specimens for CMV viral load (NOTE: if subject weighs < 650 grams, this virology specimen will not be obtained)	Hematology labs (WBC with differential, hemoglobin, platelet count)
If obtainable, CMV detection from noninvasive urine specimen (e.g., bagged, from indwelling foley catheter, excess clinical specimen, etc.)	Chemistry labs (AST, ALT)
Ganciclovir dosing information (mg/dose, dosing interval, subject weight)	Serum creatinine

* If being drawn for clinical reasons; any laboratory value obtained during the window will suffice, with an effort being made to capture the most abnormal value

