A 95% confidence interval will be constructed to evaluate the mean changes in the log of the viral load between baseline (day 1) and weeks 1, 2, 3, 4, 5, and 6. Area under the curve will be calculated for each subject's CMV viral load measurement utilizing the trapezoidal rule. These AUCs will be calculated over the entire course of drug administration. Spearman's correlations will be given for each AUC estimation and also for the AUC after baseline viral load (VL) adjustment. Analysis of variance will be used to investigate whether grouping AUCs into groups (undetected, 100-1000, 1000-10000 and ≥ 10000) would indicate any PD relationships. In addition, changes in CMV viral load from baseline over time (weeks 1 through 6) will be correlated with PK parameters. These data will provide the framework for all PD analyses, where ganciclovir exposures variables will be correlated with the response variables using linear or maximum effect PD models.

Secondary analyses: To investigate the association of secondary outcomes namely, neutropenia, CMV in urine, viral load and resistance to ganciclovir, with plasma concentration, we will utilize inference methods based on Generalized Estimating Equations (GEE) which models repeated binary data. As in the primary analysis, GEE will enable us to compare groups, investigate changes of outcomes over time, and adjust for any covariates.

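### The viral-load AUC runs over treatment courses of unequal, physician-chosen length on an unstated scale, so it mixes duration with viral response

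*Protocol*

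**What the plan says.** Protocol section 11.4 defines the summary: "Area under the curve will be calculated for each subject's CMV viral load measurement utilizing the trapezoidal rule". The next sentence sets the limits of integration: "These AUCs will be calculated over the entire course of drug administration". SAP Appendix B repeats both sentences and adds nothing.

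Two statements in protocol section 4 make those limits differ by infant. On treatment: "Duration and dose of intravenous ganciclovir therapy is made at the discretion of the treating physician". On sampling, viral loads are taken through Period 7 (Study Assessment Days 39-42) at most, and only "as long as the subject is receiving intravenous ganciclovir therapy (that is, until the ganciclovir is permanently discontinued". Section 2.1 calls duration variable and says that "anecdotal experience suggests that it generally is in the range of two to four weeks of total antiviral therapy".

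Two analyses use this AUC. The first is rank correlation: Spearman "correlations will be given for each AUC estimation and also for the AUC after baseline viral load (VL) adjustment". The other variable is not named; from the surrounding text and the secondary objective I read it as ganciclovir PK. The second is a grouped comparison: "Analysis of variance will be used to investigate whether grouping AUCs into groups", with groups undetected, 100-1000, 1000-10000 and at least 10000.

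Baseline viral load is the only adjustment named for the AUC, and its form is not given. Covariate adjustment is mentioned for the mixed models and GEE, not here. The log scale is specified for the weekly mean changes but not for the AUC. Section 11.4 also plans to correlate weekly changes from baseline (weeks 1 to 6) with PK parameters.

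**The concern.** A trapezoidal total keeps growing while sampling continues, whatever the drug does to the virus. Two infants with identical viral trajectories get different AUCs if one is treated longer. The upper limit of integration is also decided after exposure has begun, so it can itself depend on exposure.

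The documents make such a link plausible. Section 2.1 reports Grade 3 or 4 neutropenia in about two-thirds of neonates given six weeks of ganciclovir. Section 3.1 lists neutropenia as a function of PK as an objective. Section 4 returns each infant's AUC and CL to the site. If higher exposure goes with shorter treatment, total AUC falls as exposure rises even when the drug does nothing to the virus, and the correlation would be read as an exposure-response relation. At stake is one of the analyses serving the secondary endpoint that relates plasma concentrations to whole-blood viral load.

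**Working it through.** **1. The plan's own figure.** None is given for the viral-load AUC. The plan's power statement concerns ganciclovir AUC12: means 20, 20, 30, 35 have SD 6.495 around 26.25, so with SD 10, f = 0.65, lambda = 32 x 0.65^2 = 13.5, and the F test on 3 and 28 df has power 0.831. The stated 83% reproduces but does not bear on this point.

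**2. Same trajectory, different stopping day.** Area = sum of (y1 + y2)/2 x (t2 - t1), with samples on Days 1, 7, 14, 21, 28, 35, 42. The start at 4 log10, the decline and a floor of 2 log10 are assumptions.

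| Scale and course | Stop Day 14 | Day 28 | Day 42 | Ratio, 42 to 14 |
|---|---|---|---|---|
| log10, flat | 4 x 13 = 52 | 4 x 27 = 108 | 4 x 41 = 164 | 3.2 |
| log10, -0.5 per week | 46 | 82 | 110 | 2.4 |
| linear, flat | 130,000 | 270,000 | 410,000 | 3.2 |
| linear, -0.5 log10 per week | 58,355 | 65,503 | 66,965 | 1.15 |

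The scale decides how much duration matters once virus falls.

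**3. What the cut-points imply.** On the log10 scale, 6 log10 held from Day 1 to Day 42 totals only 6 x 41 = 246, so the 1000-10000 group cannot be reached. On the linear scale in days, even the falling course above exceeds 10000. The cut-points look like viral loads in linear units rather than areas.

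**4. Simulation with no drug effect.** Inputs: n = 32 (section 11.2) and durations of about 14-28 days (section 2.1) or 10-42 days (the longer reaching Period 7). Assumed: baseline mean 4 and SD 1 log10; decline 0.2 or 0.5 log10 per week, SD 0.2; measurement SD 0.3; floor 2 log10; sample days as in step 2; exposure-duration correlation 0, -0.3 or -0.5. There were 700 runs per cell, so Monte Carlo error is about 1 point near 5% and about 2 points near 50%.

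Spearman correlation of total AUC:

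| Scale, durations | with duration | with baseline load |
|---|---|---|
| log10, 14-28 days | 0.54-0.58 | 0.68-0.73 |
| log10, 10-42 days | 0.81-0.83 | 0.44-0.46 |
| linear, both | 0.04-0.16 | 0.92-0.96 |

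Rejection rate of the Spearman test with exposure, nominal 5%:

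| Scale | Exposure-duration correlation | Total AUC | After rank-regression baseline adjustment |
|---|---|---|---|
| log10 | 0 | 4-7% | 4-6% |
| log10 | -0.3 | 13-26% | 19-28% |
| log10 | -0.5 | 31-64% | 54-73% |
| linear | 0 to -0.5 | 4-7% | 4-15% |

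On the log10 scale, adjustment raises the rate because removing baseline variation leaves duration as a larger share of what remains.

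A second simulation under the same null and the same two correlations gave, on the log10 scale, 12-17% and 23-47% unadjusted and 21-26% and 47-62% adjusted. On the linear scale it gave 4-7% unadjusted and 4-11% adjusted. I use it as corroboration and to set the ends of the quoted ranges.

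**5. Candidate repairs, log10 scale.** Dividing the area by observed time gives 4-6% in eleven of twelve cells and 11% in the other (10-42 days, fast decline, correlation -0.5). Step 2 shows why it is incomplete: for the falling course the time-average minus baseline is 46/13 - 4 = -0.46 at Day 14, 82/27 - 4 = -0.96 at Day 28 and 110.2/41 - 4 = -1.31 at Day 42. A common window removes this dependence: the Day 1-14 window gave 4-7% in the second simulation, and the week-1 change gave 4-7% in the first.

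**The case against.** Four objections have weight.

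- **The scale.** The cut-points point to linear viral load. With falling virus, baseline then dominates and false positives barely rise. This stands. It does not close the matter, because the plan never states the scale, the same section uses logs for the weekly changes, and the choice decides whether the test is sound.
- **The link between exposure and duration.** No passage says that higher exposure shortens treatment; section 2.3.2 describes PK results informing dose. This also stands. The link is plausible but unquantified, and without it the error rate is nominal.
- **Weekly changes are also planned.** They do not accumulate with duration, so part of the PD analysis is free of this problem. They do not repair the AUC correlations or the ANOVA, and no analysis is named as the main one.
- **A Period 3 window loses infants.** Section 5.1 requires only three further anticipated doses, so some will stop earlier. That is a real cost of the fix.

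A reader might go further and infer that the AUC largely measures how long the physician treated. That fits only the log10 scale with widely varying durations (about 0.8). At 14-28 days the correlation with duration is about 0.55, below that with baseline, and on the linear scale with falling virus it is at most 0.16. A reader might also take the AUC correlations to be the core PD analysis, which the planned weekly-change correlations contradict. Nor can a specific loss of power be claimed: it depends on an unknown effect size and on a baseline adjustment whose form the plan leaves open.

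**Conclusion.** The point holds in conditional form. The viral-load AUC has infant-specific limits set by treatment length, nothing in the plan corrects for that length, and its scale is missing. It therefore mixes duration with response.

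On the log10 scale with an assumed exposure-duration correlation of -0.3 to -0.5, false positives at nominal 5% are about 12-64%, and about 19-73% after regression-type baseline adjustment. With no such correlation they are nominal and duration is only noise. On the linear scale with falling virus they are about 4-7%, and up to about 15% after adjustment. The viral trajectories and the exposure-duration correlations are my assumptions; the documents supply only the sample size, the sampling schedule and the rough range of durations.

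This concerns a secondary PD endpoint. It is a worthwhile, cheap improvement, not a threat to the primary AUC12 analysis.

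**What to change.** Change the wording in SAP Appendix B and protocol section 11.4:

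- State that the viral-load AUC uses log10 viral load, with a stated value for undetected results.
- For the PK correlations, use the time-averaged AUC minus baseline over a common window, first sample through Period 3: trapezoidal area divided by (last minus first sampling day), minus the first log10 value, using actual sampling days.
- Report the full-course time-averaged AUC minus baseline as a sensitivity analysis, together with the correlation of AUC with treatment duration.
- Restate the ANOVA cut-points on the same scale as the summary they divide.

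The cost is text only: no extra blood and no change to care. Later samples leave the main AUC summary. Infants who stop before Period 3 contribute a shorter window, which brings back some unequal length, or only the already planned week-1 change; the SAP should say which. Visit windows still let the common window run from 8 days (Day 3 to Day 11) to 16 days (Day 1 to Day 17), but that scatter comes from visit timing rather than from the total length of treatment.

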The appropriate dose of intravenous ganciclovir for premature babies has not been studied. Previous studies of ganciclovir have indicated that the area-under-the-concentration curve (AUC) of ganciclovir is most closely related to virologic treatment success.²³ Data from an National Institute of Allergy and Infectious Diseases (NIAID) CASG Phase II study of intravenous ganciclovir (6 mg/kg/dose q 12 hrs) in term neonates with symptomatic congenital CMV disease revealed a median AUC₁₂ of 27 μ gxh/mL (mean AUC₁₂=32.3+13.7 μ gxh/mL, range 17.2 to 55.9 μ gxh/mL, n=13).²⁴ A more recent CASG investigation of oral valganciclovir included comparative pharmacokinetic data following 6 mg/kg/dose every 12 hrs of intravenous ganciclovir. The mean AUC₁₂ in young neonates (median age: 16.5 days) on the second day following study enrollment was 38.2 μ gxh/mL (median: 25.5 μ gxh/mL), but the coefficient of variation was large (112).²⁵ In five neonates in whom pharmacokinetic sampling was performed on day 4 and day 34 of intravenous ganciclovir therapy, ganciclovir clearance nearly doubled and AUC₁₂ reduced by almost half over the 30 day interval,²⁵ suggesting that maturational changes may be occurring rapidly in early life which may affect ganciclovir dosing. No data exist on ganciclovir dosing in very premature babies, who are at greatest risk for CMV disease.

due to the absence of transplacental antibodies. Notably, acyclovir must be dose-adjusted based upon renal function such as that which can occur with prematurity.²⁶

The CASG and the UAB Central Unit have had significant success in performing multi-center pharmacokinetic and pharmacodynamic studies with both ganciclovir and valganciclovir in infants during the first month of life.^{21,22,25,27-30} In this study, this experience will be utilized to further define the utility of this drug in very premature children.

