3.2 Study Outcome Measures

3.2.1 Primary Outcome Measures

Primary Endpoint:

- Plasma pharmacokinetics parameters for ganciclovir AUC12

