11.2 Sample Size Considerations

The primary outcome used for power analysis is the area under the curve for 12 hours (AUC12) following 6 mg/kg of ganciclovir. In a one-way ANOVA design, we would like to compare the means of 4 groups (see below) with sample sizes of approximately 8, 8, 8, and 8 (32 total subjects enrolled across the four cohorts). If the means of the AUC12 of the 4 groups are 20, 20, 30, and 35 assuming a common standard deviation of 10, these mean differences (equivalent to an effect size of 0.72) will be detected at 83% power using an F test with 0.05 level of significance. In order to look at other possible scenarios, we provide the table below that looks at other standard deviation values, its corresponding effect size given the differences in means as described above, and the power of detecting such a difference/effect size. If estimating the AUC without regard to the groups, the margin of errors associated with a 95% confidence interval assuming different standard deviation values and a sample size of 32 are given in the table below.

Standard Deviation	S=8	S=9	S=10	S=11
Effect Size	0.81	0.72	0.64	0.59
Power	96%	91%	83%	75%
Margin of Error	2.33	2.62	2.91	3.20

The above parameter values were hypothesized based on results from other studies.^{25,34} It is worth noting that there are no PK data in this population and the results are likely to be different from other studies due to the maturational changes.

Following enrollment, subjects will be stratified by gestational age and by chronologic age as follows: 1) \leq 27 weeks 6 days gestational age at birth and \leq 30 days chronologic age at study enrollment; 2) \leq 27 weeks 6 days gestational age at birth and $>$ 30 days chronologic age at study enrollment; 3) \geq 28 weeks 0 days gestational age at birth and \leq 30 days chronologic age at study enrollment; 4) \geq 28 weeks 0 days gestational age at birth and $>$ 30 days chronologic age at study enrollment. The total sample size across these four cohorts is 32 subjects. Enrollment of an additional 2-3 subjects may be allowed for operational reasons. If the 32

subjects enrolled are not balanced across the 4 groups, we instead will look at the correlation between gestational age at birth. With 32 subjects, the margin of errors of a 95% confidence interval for estimating the correlation given the observed correlation values are given below.

Correlation	0.4	0.5	0.6	0.7
Margin of Error	0.6	0.542	0.47	0.38

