11.4 Final Analysis Plan

Primary analysis: To compare the ganciclovir pharmacokinetics and pharmacodynamics as measured by AUC₁₂ in premature infants with postnatally or congenitally acquired CMV infection differ from those in term neonates and older infants, we will construct 95% confidence intervals around the mean AUC₁₂ for the subjects in this study and compare these means across the groups. If there are not enough subjects in the groups, we will use the actual gestational age and correlate it with the AUC₁₂ by computing correlation coefficients and a fitting regression model. Additional pharmacokinetic parameters that compose analyses for secondary endpoints include Cmax, T1/2, CL, and VD. For measures that are repeated over time, we will utilize mixed models for repeated measures. In addition to being able to compare these outcomes for the different groups, we can also look into how these measures change over time and adjust for covariates.

Ganciclovir pharmacokinetic parameters will initially be determined using non-compartmental analysis (WinNonlin v5.3) for each individual subject. The parameters (AUC₁₂, CL, Vd, etc.) will be summarized and further used for exploratory pharmacodynamic analysis. We will also apply pharmacokinetic models to the concentration-time data, either individually or using a population approach. We may also pool these data with prior CASG 109 PK data in order to have a more robust covariate analysis across a wider range of ages.

The second pharmacokinetic analysis will utilize either population pharmacokinetic or individual modeling approaches, depending upon how much data we actually are able to collect and the nature of those data. Concentration-time data will be analyzed using nonlinear mixed-effects in ADAPT 5.0. If a population approach is employed, this will give us the opportunity to explore

relationships between ganciclovir exposure and multiple covariates, such as gestational age, weight, renal function, etc.

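### One planned viral-load analysis correlates weekly change from baseline with unspecified PK parameters, with no lead exposure, baseline adjustment or actual sampling day

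*Protocol*

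**What the plan says.** Protocol 3.2.2 lists the correlation of ganciclovir concentrations with whole-blood CMV viral load as a secondary endpoint. Several analyses in protocol 11.4 bear on it, and SAP Appendix B repeats the viral-load paragraph:

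- Each infant's viral-load AUC is taken over the whole course of drug. Spearman correlations are given unadjusted and also "for the AUC after baseline viral load (VL) adjustment".
- As an addition to this, "changes in CMV viral load from baseline over time (weeks 1 through 6) will be correlated with PK parameters".
- Linear or maximum-effect PD models relate exposure to response.
- GEE is named for viral load among other outcomes, but is described as a method for repeated binary data.
- Mixed models are promised for repeated measures, in the paragraph on PK comparisons. SAP Appendix B ties them to AUC12.

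The weekly-change sentence does not say which PK parameters it means. The primary endpoint is "Plasma pharmacokinetics parameters for ganciclovir AUC12" (protocol 3.2.1), and 11.4 adds: "Additional pharmacokinetic parameters that compose analyses for secondary endpoints include Cmax, T1/2, CL, and VD". Protocol 2.1 reports that, in earlier work, the AUC of ganciclovir "is most closely related to virologic treatment success".

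**The concern.** The weekly-change analysis leaves three choices open.

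1. **Lead comparison.** No PK parameter and no week is designated, and no multiplicity rule is given. Protocol 2.1 supplies a reason to lead with AUC, but the analysis section does not use it.
2. **Baseline.** Adjustment is written for the viral-load AUC only. An unadjusted change score carries the noise of the baseline value and is open to regression to the mean.
3. **Time.** Weeks label windows. Baseline is called day 1 in 11.4, but its window is Study Assessment Days 1 to 3 (protocol 7.2.1), and the next window is Days 4 to 10 (7.3.1). Ganciclovir may also have started before enrollment (protocol 4), so the same study week can mean different times on drug.

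At stake is how a secondary exposure-response result would be read. With no named lead analysis, a nominally significant pair picked from many could be reported as the finding.

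**Working it through.** **The plan's own figures.** The documents give no error rate or power for these correlations. The only operating figure concerns the AUC12 comparison: "If the means of the AUC12 of the 4 groups are 20, 20, 30, and 35 assuming a common standard deviation of 10", tested "using an F test with 0.05 level of significance", with 8 per group and stated power 83%. It reproduces:

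- The mean of the four means is 26.25. The squared deviations sum to 39.06 + 39.06 + 14.06 + 76.56 = 168.75, so the SD of the means is √(168.75/4) = 6.50 and f = 0.65.
- The noncentrality is 32 × 0.65² = 13.5. The noncentral F(3, 28) gives 83.1%.

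This says nothing about the viral-load analysis. The 0.05 level used below is an assumption.

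**Number of pairs.** AUC12, Cmax, T1/2, CL and Vd make 5 parameters. Over 6 weekly changes that is 5 × 6 = 30 pairs. If treatment lasts at most four weeks, it is 5 × 4 = 20; protocol 2.1 puts usual treatment at two to four weeks, and sampling stops when ganciclovir stops (protocol 4).

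**Chance of at least one nominal finding under the null, each pair at two-sided 0.05.**

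- Independent: 1 − 0.95³⁰ = 78.5%. Expected false positives: 30 × 0.05 = 1.5.
- The pairs are not independent. AUC12 and CL are reciprocal given dose, T1/2 follows from Vd and CL, and all changes share one baseline. The range was therefore simulated with Spearman tests, 2,000 null trials per six-week scenario. None of the following inputs is in the documents: log-scale SD 0.4 for CL, 0.3 to 0.4 for Vd and 0 to 0.3 for dose; CL–Vd correlation 0 or 0.3; typical half-life 3 h; serial correlation of viral load 0.3 to 0.9.

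| Scenario | Infants per week | P(at least one) | Expected false positives |
|---|---|---|---|
| Six weeks, complete | 32 throughout | 41% to 58% | about 1.5 to 1.6 |
| Six weeks, assumed attrition | 32, 28, 22, 16, 10, 8 | 50% to 67% | about 1.5 to 1.6 |
| Four weeks, complete | 32 throughout | 40% to 49% | about 1.0 |
| Four weeks, assumed attrition | 32, 32, 21, 11 | 43% to 51% | about 1.0 |

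The four-week rows use serial correlation 0.5 to 0.7. They can fall somewhat below 40% when dose per kg hardly varies. Their expected count agrees with 20 × 0.05 = 1.0.

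**Baseline adjustment.** Take equal variances σ² and correlation r between baseline and follow-up. The change score has variance 2(1 − r)σ², and the baseline-adjusted residual has (1 − r²)σ². The ratio is 2/(1 + r), so the proportional cut is (1 − r)/2:

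- r = 0.5: ratio 1.33, cut 25%.
- r = 0.7: ratio 1.18, cut 15%.

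The documents give no value of r. The formula also takes exposure to be unrelated to baseline.

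**Timing.** The shortest first interval is Day 3 to Day 4, 1 day. The longest is Day 1 to Day 10, 9 days.

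**The case against.** The strongest reply is that the weekly correlations are a supplement. A reader might infer that viral response is related to exposure only through unadjusted weekly changes; the documents do not support that. The same paragraph plans a whole-course viral-load AUC with baseline adjustment, and PD models, so information across weeks is used elsewhere. A reader might also take 30 separate tests as planned. The text lists no parameters for this sentence, sets no level, and could be read as one analysis over time. Protocol 11.4 calls the PD work exploratory, and 2.2 disclaims conclusions on efficacy. Footnote k of Appendix A asks for 72 hours between viral loads in different periods where possible, so a 1-day interval is an extreme.

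Baseline adjustment is not a free gain either. Exposure is not randomised, dose may be changed once PK results are returned (protocol 4), and baseline may already be on treatment. Adjusting for an on-treatment value can remove part of the exposure effect, so the two analyses may then answer different questions.

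All of this limits the size of the point. It does not remove it, because the other analyses do not clearly close the gap. The viral-load AUC is taken over courses of differing length, with no stated scaling for duration. The mixed models sit with the PK comparisons, GEE is described for binary data, and the PD models name no exposure, baseline term or time term. None is designated as the analysis of the secondary endpoint, and the 72-hour spacing is only a preference.

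**Conclusion.** The point holds in limited form and should be fixed; it does not threaten the primary objective. One of several planned PD analyses leaves the exposure measure, baseline adjustment and timing open for a secondary endpoint.

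If every pair were tested at 0.05, the null chance of at least one nominal finding is roughly 40% to 67%, with about 1.0 to 1.6 expected. The 79% figure applies only under independence, which these parameters cannot satisfy. A reader might conclude that a chance finding is more likely than not; that is not established, since several plausible scenarios fall below one half.

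The 15% to 25% cut in single-week residual variance is conditional on r of 0.5 to 0.7 and on exposure unrelated to baseline. It should not be read as a known loss of information in this trial.

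**What to change.** In protocol 11.4 and SAP Appendix B, name one lead analysis for this secondary endpoint: a repeated-measures mixed model of follow-up log10 viral load on

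- baseline log10 viral load,
- actual day since the first ganciclovir dose,
- log AUC12, and
- AUC12-by-day, stated in advance as the lead coefficient.

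Use a random infant intercept, and add a random slope only if the data support it. Treat values below the detection limit as censored. Report the other PK parameters and the single-week correlations descriptively, and the unadjusted change analysis as a sensitivity analysis. Because protocol 3.2.2 words the endpoint as a correlation, add a sentence saying that this model addresses it.

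**Cost.** Wording in two documents, with no new samples or procedures. Viral load, AUC12 and the ganciclovir start date are already collected; I assume that each specimen's collection date is recorded.

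**Downsides to state.** The model assumes a shape of decline, which a curvature term can check. Each infant gives few follow-up values, follow-up ends when treatment stops, and baseline may be on treatment, which is why the unadjusted analysis should stay visible.
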